2.0 BACKGROUND AND RATIONALE

2.1 Rectal cancer and standard treatment

Rectal cancer is a common cancer with about 2000 new patients diagnosed yearly in Sweden. Survival and risk for local recurrence (5-9%) have improved over the last decades due to both improved surgical technique and preoperative treatment (1-7).

Standard primary radical surgery (Total Mesorectal Excision (TME)) is the evidence-based oncologically effective treatment for early-stage rectal cancer; only 2% and 12% of patients experience local or distant failure respectively (2). It entails removing the bowel including the surrounding fat and lymphatic tissue (mesorectum). However, resection of a low rectal tumour may require a permanent stoma, and many more patients will need a temporary stoma, some of which are not reversed. Complications associated with rectal cancer surgery include anastomotic leakage, which is a common complication even in non-irradiated patients, as clinical leaks amounted to 16% in the Dutch TME trial (8). Pelvic dissection may inadvertently cause autonomic nerve damage leading to urinary incontinence or retention (25%-34%) and sexual dysfunction (9-11). More than half of all patients experience some form of faecal incontinence following primary TME surgery and 30-40% suffer daily symptoms of urgency, incomplete emptying and stool frequency (12-14).

It is possible that radical surgery, may not be the optimal method of treatment for early tumours. Early rectal tumours can be locally excised through the anus with low morbidity and mortality using Transanal Endoscopic Microsurgery (TEM) or endoscopic submucosal dissection (ESD) (15). Morbidity and mortality after local excision are lower than after radical resection, but the long-term results have been inadequate with local recurrence rates ranging from 5% to 28% for T1 lesions, and from 11% to 45% for T2 lesions (16, 17). The problem is that these rates of recurrence are higher than would be expected with radical resection, although some registry-based data indicate that appropriate right selection of patients might improve these results (18). Omission of total mesorectal excision risks leaving behind microscopic lymph node metastases, a potential cause of local failure. It is difficult to predict the risk of lymph node involvement although there is data indicating that the risk increases with depth of wall penetration, but there can be lymph node involvement even in patients with only T1 tumours, risk factors for this includes lymphovascular invasion, tumour budding and perineural invasion. The incidence of lymph node metastasis ranges from 6% to 14% for T1 tumours, 17% to 23% for T2 tumours, and 49% to 66% for T3 tumours (19).

2.2 Neoadjuvant (chemo)radiotherapy

Neoadjuvant (preoperative) radiotherapy has been shown to reduce local recurrence in several randomized trials (20). The two most common schedules for this treatment are preoperative chemoradiotherapy (45-50.4 Gy in combination with fluoropyrimidine based chemotherapy) and short course hypofractionated radiotherapy (25Gy in five fractions). No significant difference in local recurrence rates has been reported between the two types of schedules (21, 22). Short course radiotherapy with a delay to surgery has been studied in the Stockholm III trial which demonstrated low toxicity and a 12.5% pathological complete response (pCR) rate (23).

Although the main aim of neoadjuvant treatment firstly is to reduce the risk for local recurrence after surgery, achieving a complete removal of the tumour, a pathological

complete response (pCR) is sometimes possible. Data indicates that if a pathological complete response is achieved disease-free survival is improved compared to patients with no or little response to neoadjuvant treatment (24-26).

It has been suggested that if a clinical complete response (cCR) is achieved, surgery is not necessary, and a strategy of organ preservation could be adopted. However, the neoadjuvant must treatment eradicate all tumour tissue to achieve organ preservation. In more advanced rectal cancer this occurs after neoadjuvant treatment in about 15-20% of all tumours, thus making deferral of surgery possible. This is mainly referred to as *opportunistic* organ preservation performed in Sweden only within the framework of a study protocol (the WoW study, NCT03125343).

In Brazil this approach has been tested in selected cases since 2004 (27). It has since been reported in selected cases from all over the world collected in an international watch and wait registry, indicating that it can be possible to defer surgery if signs of cCR are seen after neoadjuvant treatment (28). In a pooled dataset including 2323 patients a correlation was found between the clinical T-stage and the pCR rate (cT1: 58%, cT2: 28%, cT3: 16% and cT4: 12%) (25). Thus, the success rate of achieving a clinical complete response after radiotherapy treatment will be highly dependent upon tumour stage. The data indicate that with appropriate selection neoadjuvant treatment may be of particular benefit to patients with early tumours.

2.3 Neoadjuvant treatment in early rectal cancer with the aim to avoid surgery

There have been some studies, mainly prospective, non-randomised phase II studies that have evaluated use of (chemo)radiotherapy in the context of early-stage rectal cancer for the purpose of achieving a clinical complete response and organ preservation. These studies generally supplemented the neoadjuvant treatment with local transanal excision and or radiotherapy boosts of the area of the bowel wall originally occupied by tumour. The studies demonstrated high rates of organ preservation and infrequent pelvic cancer recurrence; but often at the cost of treatment related toxicity (29-34). It has been suggested that modifying the approach to local excision could improve results, either only performing local excision if residual tumour is present as carried out in the recent STAR-TREC trial (35) or in all patients (sometimes only removing a scar) as in the recently published TAUTEM (Chemoradiotherapy and Local Excision vs Total Mesorectal Excision in T2-T3ab, N0, M0 Rectal Cancer). In the TAUTEM study 17 hospitals in Spain participated and all but one patient in the chemoradiotherapy arm underwent TEM(36). In the STAR-TREC trial both chemoradiotherapy and short course radiotherapy with a delay to surgery was used(35) and patients with incomplete response were treated with TEM if there were signs of a more advanced tumour, these patients were referred to radical surgery. Three centres in Sweden participated in the study and results presented at the ESTRO congress in Vienna report cCR after 5x5 Gy of 27% compared to 57% after CRT. Addition of local excision after near complete response resulted in a watch and wait strategy at one year of 61.5% after 56x5Gy compared to 79.8% for patients treated with CRT.

Another option that has been suggested consists of an endoluminal brachytherapy approach which might achieve better tumour response with lesser toxicity (37). The OPERA included patients with T2-T3b tumours with minor lymph node involvement (N1<8 mm) and all patients received chemoradiotherapy. They were then randomized to either a boost of external

beam radiotherapy (9 Gy \times 5) or brachy radiotherapy (90Gy/3 fractions). They found that 64% of patients with external beam radiotherapy achieved a clinical complete response, compared to 92% after brachy radiotherapy. The 5-year local regrowth was 39% vs 17%, and some patients had their local regrowth after 3 years, indicating that long-term follow-up may be necessary. There are indications that patients that undergo brachy radiotherapy and then have incomplete response have very poor bowel function suggesting that studies are required to ascertain that patients receive correct information for shared decision making (38).

In summary there seems to be sufficient evidence that some patients will achieve clinical complete response after chemoradiotherapy with a long-term positive oncologic outcome (25), but long-term morbidity is not sufficiently described to date. This treatment will increase the risk for postoperative complications and increased risk for affected bowel function after both local excision and TME-surgery. Local excision may not always be adequate to treat insufficient response to chemoradiotherapy. Presently in Sweden there are no available treatment options apart from radical surgery (as recommended in the Swedish National Treatment Guidelines for Colorectal cancer) for patients with early rectal cancer while waiting for the long-term results from the STAR-TREC trial. The CORRECT trial has commenced in Stockholm and Uppsala in 2025 offering treatment options with contact therapy (brachy radiotherapy).

2.4 Rationale and design of the Next generation study awaiting the results from the STAR-TREC study

In light of the promising results from smaller studies, and the positive experience from treatments centres within the STAR-TREC trial this study aims to offer a treatment option to patients with early rectal cancer in a prospective phase II study to enable evaluation of results, and to enable comparisons with results from present and future studies until results from the STAR-TREC trial are published. The first results presented at ESTRO 2025 indicate that 57% of patients that received CRT maintained a clinical complete response one year after treatment compared to 27.3% in the arm with 5 \times 5 Gy (<https://user-swndwmf.cld.bz/ESTRO-2025-Abstract-Book>). The dosage of Capecitabine at 825mg/m² for five days per week has been chosen to mimic the STAR-TREC study.

The STAR-TREC trial included patients with a radiological staging Magnetic Resonance Imaging (MRI)-stageTX/T1-3b, NX/N0, MX/M0 rectal tumour. Exclusion criteria were designed to avoid including patients with known risk factors for locoregional relapse following rectal cancer treatment. This study will use the same inclusion criteria, and similar follow-up routine. Patients who choose standard treatment i.e. radical surgery (TME-surgery) will be the control arm.

The choice to refrain from local surgical resection of a possible small regrowth or insufficient response lies in a combination of clinical observations of morbidity and insufficient clinical experience at the study sites. It may be reconsidered when the long-term results from the STAR-TREC study are available, and the use of local excision is supported by the recent data from the TAUTEM trial where mesorectal CRT and TEM were found non-inferior to standard TME resection (36).

2.1.5 Patient involvement

The study has been discussed and modified in collaboration with patient representatives from the Swedish stoma association ILCO.

3.0 BENEFIT-RISK EVALUATION

3.1 Benefits

The possible benefits for patients entering this study include

- avoiding surgery and surgery related complications including surgical infections, small bowel obstruction, cardiopulmonary complications and others
- possibly improved bowel function due to deferring surgery
- possibility to avoid a stoma that may improve quality of life.

3.2 Risks

Possible risks are:

- Patients enter the study hoping to avoid surgery, but many will still require surgery to achieve cure. This could be difficult to accept and may lead to disappointment. The best way to mitigate this is probably by informed consent and providing support.
- As some patients will require surgery it could be considered that they are over-treated with chemotherapy and radiotherapy before surgery. This may increase the risk for complications postoperatively.
- The rigid follow-up if surgery is avoided in a watch and wait setting might increase the risk of fear of recurrence or anxiety, although data are scarce (39, 40). This is mitigated by support and information.
- Chemotherapy may induce side-effects: hand-foot syndrome, diarrhoea, vomiting, nausea, stomatitis, abdominal pain, anorexia, fatigue, and asthenia. Less common side effects include cardiotoxicities, cytopenia, infections, thrombophlebitis, deep vein thrombosis, pulmonary embolism, kidney failure, liver toxicity, skin reactions, hypersensitivity reactions and toxic leukoencephalopathy.
- Radiotherapy of rectal cancer, 50 Gy/25 Gy, can cause acute and late side-effects such as increased urinary and bowel frequency, pain in the lower abdomen and anus, anal discharge, sexual dysfunction, infertility, colitis, pelvic stiffness/pain, secondary malignancies. In this study, the treatment volume is significantly smaller compared with radiotherapy given in advanced rectal cancer. The concept of reduced treatment volume is new and previously tested only in the STAR-TREC trial, preceding this study. Interim data from the STAR-TREC trial show minimal short-term treatment-related toxicity. In patients that have a complete tumour response with radiotherapy alone, the overall risk of late morbidity is assessed to be lower compared with the patients undergoing up-front TME-surgery according to clinical routine. In patients that will need TME surgery after radiotherapy the radiotherapy will add up to the acute and late morbidity. Given the reduced treatment volumes and moderate radiotherapy doses, the acute and late toxicity is assessed to be manageable.

4.0 TRIAL OBJECTIVES

Investigate if using chemoradiotherapy 2 Gy x 25 with Capecitabine 825 mg/m² and a limited clinical target volume (CTV) will obtain a clinical complete response rate of 50% or more in patients with TX/T1-3b, NX/N0, MX/M0 rectal tumours.

The aim is to provide a treatment option to surgery to patients with early rectal cancer that fulfil the inclusion criteria for the now closed STAR-TREC study. This will enable a safe implementation with a control of outcomes and treatment regimens.

4.1 Primary objective

The primary objective of this trial is to achieve a sustained clinical complete response rate in patients 1 year after treatment.

4.2 Secondary objectives

The secondary objectives of this study include oncologic safety, treatment related safety and functional outcome including quality of life (QoL).

4.3 Primary endpoint

Primary variable: clinical complete response rate. Measured as the ratio of patients with a non-operative approach at onset that after evaluation by a combination of MRI, clinical and endoscopic examination have a clinical complete response at 1 year.

4.3. Secondary endpoint

The secondary endpoints for the study are:

- Oncological:
 - local recurrence
 - local regrowth
 - Survival (overall)
 - Metastases
 - Organ preservation rate
 - clinical complete response rate
- Surgical
 - morbidity measured with Comprehensive Complications Classification Index (41)
 - total length of hospital stay,
 - radical resection (R0) after surgery
- Quality of life
 - Urinary function
 - Sexual function
 - Bowel function
 - presence of a stoma
- Health economic evaluation.

5 TRIAL DESIGN AND PROCEDURES

5.1 Overall trial design

The study design is a national multi-centre prospective non-randomized phase IV cohort study. Planned centres are Sahlgrenska University Hospital, Skåne University Hospital, Stockholm South General Hospital. It is an initiative from the surgical and oncological community in Sweden to offer patients a choice of treatment before solid scientific evidence is present to support either treatment option. It is a low-intervention clinical trial as the investigational medicinal product Capecitabine is authorized and used according to the terms in its marketing authorization to the same diagnosis but at a different tumour stage than standard. The complementary diagnostic procedures are not considered to contribute to the risk or burden to subject safety compared to normal clinical practice.

Patients who meet inclusion criteria will be offered neoadjuvant treatment to defer/avoid surgery or TME surgery upfront.

Those who prefer organ preservation will be treated with **mesorectal chemoradiotherapy**.

Those who prefer standard surgery or have no preference, will undergo standard TME surgery without neoadjuvant treatment. They will be asked to participate in the QoL part of the study, while the remainder of the data will be extracted from the national quality registry, the Swedish ColoRectal Cancer Registry (SCRCR)

For possible organ preservation long course concurrent chemoradiation will be performed (CRT):

Capecitabine: 825 mg/m² orally, b.d., on radiotherapy days

Radiotherapy: A dose of 50 Gy applied to the primary tumour and surrounding mesorectum in 25 fractions of 2 Gy, 5 days a week.

The **first assessment after treatment is at 6-8 weeks** (from end of chemoradiotherapy) using composite clinical, endoscopic and MRI based assessment will identify the minority of non-responders who should convert to TME surgery. Patients demonstrating a clinical complete response (cCR) after chemoradiotherapy 6-8 weeks will be offered to enter the national watch and wait program and followed accordingly in the WoW study NCT03125343 with endoscopy and MRI and clinical follow-up accordingly (at present 3, 6, 9, 12, 15, 18, 21 and 24 months and then every 6 months for another 3 years and then yearly for five more years).

If **near complete response** there will be a re-evaluation after **12 weeks** after chemoradiotherapy to determine if the criteria for clinical complete response (cCR) are met.

Patients who achieve cCR may progress directly to active surveillance and included in the Swedish Watch and Wait study (WoW, NCT03125343). Clinical and radiological follow-up at 3, 6, 9, 12, 15, 18, 21 and 24 months. First year registered in CRF in this study too, after that follow-up at 1, 2 and 3 years.

Those who do not fulfil the criteria for cCR will progress to TME-surgery. Follow-up at 1, 2 and 3 years.

Time points for follow up and collection of data into CRF

1. Inclusion
2. Start of neoadjuvant treatment
3. Evaluation after neoadjuvant treatment
4. Second follow-up after neoadjuvant treatment if applicable
5. Third follow-up after neoadjuvant treatment if applicable
6. Surgery if applicable
7. Postoperative hospitalization if applicable
8. 1 month follow-up after surgery
9. 1 year after diagnosis
10. 2 years after diagnosis
11. 3 years after diagnosis
12. 5 years only through SCRCR and Swedish Cause of Death Registry

5.2 Procedures and flow-chart

See table 1 for details on each visit.

Each follow-up visit may vary 2-3 weeks depending on availability to radiology, endoscopy and clinical visit.

Trial ID: NG-ST
Version No: 1.1
Date: 10 December 2025
EU Trial Number: 2025-522955-25-00

432

	Screening	Neoadjuvant treatment				Surgery if applicable ⁴		Follow-up				435
	At/before first visit in surgical clinic	First visit in oncology clinic	End of CRT treatment	6-8 weeks after end of neoadjuvant treatment if not cCR	10-12 weeks after end of neoadjuvant treatment if not cCR	Surgery	Hospital stay after surgery, follow-up 1 month after discharge	3 months after cCR	6 months after cCR	9 months after cCR	12 months after cCR or surgery	Every 3 months 12-24 months after cCR
Written informed consent	X											441
Medical history ¹	X											442
ECOG performance status	X		X									443
Digital rectal examination	X			X	X			X	X	X	X	X
Physical examination	X											444
Colonoscopy ²	X											445
Confirmed diagnosis of adenocarcinoma ³	X	X										446
Computerized Tomography (CT) scan thorax, and CT or MRI abdomen	X										X	447
High resolution MRI pelvis	X			X	X			X	X	X	X	448
MDT review	X											449
Blood sample	X					X						450
Preparation of FFPE tissue blocks and biopsies ³	X					X						451
QoL questionnaire	X			X							X	452
Toxicity related to (chemo)radiotherapy registered in CRF			X					X				453
Complications related to surgical procedure according to Clavien-Dindo												454
Sigmoidoscopy								X	X	X	X	X
Survival status		X	X				X	X				456

459
460
461
462

history includes details of current colorectal cancer, previous and current medical conditions and previous treatments received. ² Colonoscopy should be performed either prior surgery or within three months after surgery. At least one colonoscopy to be performed within the first 3 years of follow-up and according to national guidelines. ³ Biopsies taken and sent to routine pathology department (note name of pathology department in CRF). ⁴ Surgery can be performed either immediately or when a cCR cannot be achieved or if there is suspicion of regrowth.

Trial ID: NG-ST
Version No: 1.1
Date: 10 December 2025
EU Trial Number: 2025-522955-25-00

Follow-up

Not registered in eCRF but according to clinical routine

Not registered in eCRF but according to clinical routine

Not registered in eCRF but according to clinical routine

Not registered in eCRF but according to clinical routine

	15 months after cCR	18 months after cCR	24 months after cCR or surgery	30 months after cCR	36 months after cCR or surgery	42 months after cCR	48 months after cCR	54 months after cCR	60 months after cCR
Written informed consent									
Medical history ¹									
ECOG performance status									
Digital rectal examination	X	X	X	X	X	X	X	X	X
Physical examination									
Colonoscopy ²									
Confirmed diagnosis of adenocarcinoma ³									
Computerized Tomography (CT) scan thorax, and CT or MRI abdomen			X		X		X		X
High resolution MRI pelvis	X	X	X	X	X	X	X	X	X
MDT review									
Blood samples			X		X				
Preparation of FFPE tissue blocks and biopsies ³									
QoL questionnaire			X	X	X				
Toxicity related to (chemo)radiotherapy registered in CRF			X		X				
Complications related to surgical procedure according to Clavien-Dindo									
Sigmoidoscopy	X	X	X	X	X	X	X	X	X
Survival status	X	X	X	X	X	X	X	X	X

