9.2.2 Assessment of intensity

Patients should be reviewed at least weekly during CRT to perform an assessment of acute toxicity. Remote toxicity assessments (e.g. over the telephone) are allowed as per local practice 4. The local team should have a structure in place that ensures that patients experiencing side effects can be seen and undergo review.

The following guidance should be followed for the management of acute toxicity and dose modifications:

- Adverse Events (AEs) should be graded according to the NCI Common Terminology Criteria for Adverse Events version 4.03 (CTCAE v4.03)
- In the event of overlapping toxicities, dose modification should be based on the worst toxicity grade observed.
- All dose modifications should be documented with clear reasoning and documentation of the approach taken in the CRF and in the medical notes.
- If a patient experiences a toxicity, then dose modifications should be applied as specified in the protocol section 8.3.7.
- **In the event of a second episode of the same grade ≥ 3 toxicity, capecitabine should be permanently discontinued.**

Dose modification and toxicity should be managed according to local routines. Details on toxicity is registered in CRF.

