9.3 Reporting and registration of Adverse Events

NOTE! In this study the following events are not reported as an AE or SAE:

- Planned surgery (e.g. TME surgery or stoma reversal)
- Planned hospitalization
- Recurrence
- Death due to progression of the disease

At each trial visit, adverse events (AE) are registered, starting after study start, up to and including one year after the subject has entered the study. All AE that occurs during the trial and which are observed by the investigator/trial nurse or reported by the subject will be registered in the CRF regardless of whether they are assessed as related to the investigational medicinal product or not. Assessment of causal relationship, severity, and whether the AE is considered to be an SAE will be made by the investigator directly in the CRF. At minimum for each AE/SAE, a description of the event is recorded (diagnosis/symptom if diagnosis is missing), start and stop dates, causal relationship, severity, if the AE is considered to be an SAE, measures and outcome.

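### Between end of CRT and 24 months, the only mark for the dedicated CRT toxicity item is in a responders-only column, so toxicity is ascertained unequally by response

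*Protocol*

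**What the plan says.** All references are to the protocol.

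- **Table 1 (section 5.2), first page.** The row "Toxicity related to (chemo)radiotherapy registered in CRF" carries two marks: end of CRT, and three months after cCR. It has none at 6-8 weeks, 10-12 weeks, surgery, the postoperative stay with its one-month follow-up, or the visit headed "12 months after cCR or surgery".
- **Table 1, continued.** The row is next marked at "24 months after cCR or surgery", and then at the corresponding 36-month visit.
- **Section 5.1.** On patients without a complete response: "Those who do not fulfil the criteria for cCR will progress to TME-surgery. Follow-up at 1, 2 and 3 years".
- **Section 9.3.** "At each trial visit, adverse events (AE) are registered, starting after study start, up to and including one year" after entry, whatever the response. The CRF entry includes dates, causality, severity and outcome.
- **Section 9.1.1.** Only grade 3 or 4 events that are spontaneously reported or observed are recorded. Section 9.3 says that all AEs are.
- **Section 9.2.1.** The investigator's causality duty concerns the investigational medicinal product. Section 7.1 names capecitabine as the only one.
- **Section 9.2.2.** "Dose modification and toxicity should be managed according to local routines. Details on toxicity is registered in CRF".
- **Section 4.2.** Treatment-related safety is a secondary objective.

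**The concern.** The one mark for the dedicated item between end of CRT and 24 months depends on having reached cCR, which is the basis of the primary endpoint. Responders get a targeted toxicity record in that interval. Patients who fail CRT and go on to TME do not.

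The latter group matters most for the safety objective. Section 3.2 says that in patients who need TME the radiotherapy adds to acute and late morbidity, and that the reduced-volume approach is new. Section 8.2 refers safety measurement back to section 8.1, whose list of secondary endpoints has no CRT toxicity endpoint. Much of the safety objective therefore rests on this row and on AE registration. If the two groups are ascertained differently, a toxicity summary over all treated patients mixes two intensities of recording, with the thinner one in the patients expected to carry the greater burden.

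**Working it through.** **Step 1: marks between end of CRT and 24 months, by pathway (Table 1).**

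| Visit | Applies to a patient who never reaches cCR? | Dedicated toxicity item marked? |
|---|---|---|
| End of CRT | yes | yes |
| 6-8 weeks | yes | no |
| 10-12 weeks | yes | no |
| Surgery; stay and 1 month | yes | no |
| 3 months after cCR | no | yes |
| 6 and 9 months after cCR | no | no |
| 12 months after cCR or surgery | yes | no |
| 15 and 18 months after cCR | no | no |
| 24 months after cCR or surgery | yes | yes |

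Strictly between end of CRT and 24 months, responders have 1 mark and never-responders have 0. Neither group has one at 12 months.

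The columns appear to be read correctly: the MRI, quality-of-life and blood-sample rows all fall on sensible visits under the same alignment.

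**Step 2: what AE registration covers.** Section 9.3 applies to both groups at each trial visit for one year from entry. For a never-responder this includes 6-8 weeks, 10-12 weeks, surgery and one month after discharge. Two limits remain:

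- If the grade limit in 9.1.1 governs, grade 1-2 events are not captured by this route.
- The stated causality duty concerns capecitabine. Some category definitions in 9.2.1 add the word intervention, but the Table 1 row is the item that expressly names radiotherapy.

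I assume that the dedicated item takes all grades. Its content is in an appendix that is not shown.

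**Step 3: length of the interval for a never-responder.** The protocol gives 5 weeks of CRT and response assessment 6 to 12 weeks later. I assume 2 to 6 weeks from entry to CRT start and 2 to 8 weeks from assessment to surgery. I take 24 months as 104.4 weeks, one year as 52.2 weeks and a month as 4.345 weeks.

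- Short case: CRT ends at week 2 + 5 = 7; surgery at 7 + 6 + 2 = 15; 24-month mark at 15 + 104.4 = 119.4. From end of CRT: (119.4 − 7) / 4.345 = 25.9 months. From the end of AE registration: (119.4 − 52.2) / 4.345 = 15.5 months.
- Long case: CRT ends at week 6 + 5 = 11; surgery at 11 + 12 + 8 = 31; mark at 31 + 104.4 = 135.4. From end of CRT: (135.4 − 11) / 4.345 = 28.6 months. From the end of AE registration: (135.4 − 52.2) / 4.345 = 19.1 months.

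So there are about 26 to 29 months without the dedicated item. The last 15 to 19 of these have no scheduled AE registration either. That later stretch is not specific to non-responders: responders also lack a 12-month mark.

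**Step 4: upper bound on the share affected.** Section 2.4 gives 57% maintaining cCR at one year after CRT. Then 1 − 0.57 = 0.43.

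- With the 82 patients of section 10.1: 0.43 × 82 = 35.3, about 35.
- With the synopsis range of 60 to 80: 0.43 × 60 = 25.8 and 0.43 × 80 = 34.4, about 26 to 34.

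This counts everyone not in cCR at one year. Patients who reach cCR and later regrow can have the three-month record, so the share who never reach cCR is smaller. The protocol gives no figure for it.

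**The case against.** The strongest reply is that non-responders are not left unobserved, and this largely stands. A reader might infer from Table 1 that they have no scheduled toxicity record at all, or that toxicity after CRT would be described in responders only. The protocol supports neither reading:

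- Section 9.3 schedules AE registration, with severity and causality, for every patient in the first year.
- The 24- and 36-month toxicity marks include operated patients.
- The quality-of-life questionnaires (section 8.1.3) go to all patients, and the section 8.1.2 functional outcomes drawn from them include bowel, urinary and sexual function.
- Surgical complications are collected to 90 days (section 8.1.2).

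The response-dependent difference in the schedule is one mark.

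A second reply is that absent marks in this table are weak evidence. The Clavien-Dindo row is empty although complications are an endpoint, and sigmoidoscopy is unmarked at the response assessments although endoscopy is part of them. A mark lost in reading the PDF cannot be fully excluded. However, the toxicity row has marks on both pages, and they fall on identifiable visits. If the table is only approximate, that is itself a reason to correct the row.

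A third reply is that the grade limit in 9.1.1 affects both groups. That is true of AE registration. The inequality arises because only responders have the dedicated item to supplement it.

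**Conclusion.** The point holds in a limited form. As Table 1 stands, CRT patients who never reach cCR have no dedicated (chemo)radiotherapy toxicity item from end of CRT to 24 months after surgery, and no CRT patient has one at 12 months. AE registration partly fills the first year. Given the grade limit in 9.1.1 and the causality wording in 9.2.1, it does not make ascertainment of lower-grade and radiotherapy-related toxicity equal across response groups.

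The 43% (about 35 of 82) is a ceiling and should not be read as the expected share affected. Nor does it follow that the cohort's toxicity results would be uninterpretable: grade 3-4 events in the first year are scheduled for everyone.

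The conclusion assumes that the marks were read correctly from the PDF, that the dedicated item records more than grade 3-4 events, and that sites follow Table 1 as written. It is worth correcting because treatment-related safety is a stated objective and the change is small.

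**What to change.** 1. In Table 1, mark the toxicity item for every patient who started CRT at the 6-8 week assessment and at the existing visit 12 months after cCR or surgery. Keep the end-of-CRT, 24- and 36-month marks, and treat three months after cCR as an extra record for responders.
2. Align the header of the 6-8 week column, which restricts it to patients without cCR, with section 5.1, where all CRT patients are assessed at that time.
3. Reconcile the grade 3-4 limit in section 9.1.1 with section 9.3, so that sites know which events to record.

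The cost is an edit to Table 1 and to the AE wording, plus an existing CRF item completed at two visits that already take place. No new visit or procedure is needed; the downside is slight extra data entry.
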